LVADs have been implicated as one of the key causes of allosensitization in patients awaiting cardiac transplantation. Contemporary data on allosensitization triggered by CF-LVADs are limited, and whether allosensitization attributes to CF-LVADs affects outcomes after transplant remains controversial (33). In a recent study, an adjusted multivariable Cox regression analysis included the variables of LVAD implantation, leukocyte-filtered packed red blood cell and platelet transfusion, and sex; it found that LVAD implantation was the only independent predictor of sensitization (34). Significant allosensitization developed in 22% of the patients who received LVADs, with calculated panel reactive antibodies (PRA) > 10%.

The effect of on-pump versus off-pump implantation has not been studied, yet. However, several investigators found reduced blood loss or less need for transfusions after off-pump cardiac surgery (35). The reduction of the number of transfusions with off-pump LVAD surgery could potentially attenuate the development of antibodies to blood products that would make future transfusions and heart transplantation less difficult.

METHODS

STUDY DESIGN AND PATIENTS

LVAD-ON-OFF is a single center, two-arm, parallel-group, individually randomized (1:1) controlled trial with blinded outcome assessment (at 30 days, 6 months and 1 year) which aims to compare adverse events after off-pump versus on-pump LVAD implantation.

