- The patient has peri/postpartum cardiomyopathy, or is a pregnant or lactating woman, or a woman of child-bearing age not using a suitable method of contraception.
- The patient, who in the absence of an ICD (or any implanted device capable of defibrillation), has a history of malignant ventricular arrhythmia or sustained ventricular tachycardia (VT), with sustained VT demonstrated by QRS complexes wider than 120 milliseconds, lasting more than 30 seconds, and with a rate of more than 100 beats per minute on screening ECG or other data supporting this diagnosis.
- Recent history of psychiatric disease, including drug or alcohol abuse, that is likely to impair, in the opinion of the investigator, the subject's ability to comply with protocol-mandated procedures.
- Participation in any other clinical investigation that is likely to confound study results or affect study outcome

DEFINITION OF OUTCOME MEASURES

Primary Outcome Measures

Occurrence of the composite outcome of moderate or severe RV dysfunction (perioperative right heart failure), severe renal dysfunction requiring renal replacement therapy, thrombotic complications or death from any cause within 30 days post LVAD implantation, defined as:

- **Perioperative RV failure** is defined by the INTERMACS scoring as the need for intravenous inotropes for >14 days post-operatively or a right ventricular assist device (RVAD) (37). Right ventricular function will be measured by tricuspid annular plane systolic excursion (TAPSE) values assessed using echocardiography prior to implantation (baseline), 14 (+/- 2 days) days post-implant, 30-days post-implant, 6-months and 1-year post-implant. Additionally, we will collect also hemodynamic evidence of RV dysfunction with: a right-atrial pressure (RAP): pulmonary capillary wedge pressure (PCWP) ratio of ≥ 0.67 .
- **A thrombotic complication** is defined as any thromboembolic event (transient ischemic attack or stroke objectively confirmed with computed tomography) or confirmed pump thrombus as previously done (38). A suspected pump thrombosis event in which a thrombus is confirmed in

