the blood contacting surfaces of device inflow cannula or outflow conduit or grafts. This will be reported via direct visual inspection (documented by a photograph if available) on pump removal or by sending the pump back to manufacturer for evaluation. Any pump explanted for suspected device thrombosis will be sent back to manufacturer for analysis. All pump thrombosis events will be adjudicated by an independent committee, the Research Review Committee which is described below in the Data and Safety Monitoring Section.

- For patients who will **die in the hospital within 30 days**, the cause of death will be confirmed by postmortem examination performed by a pathologist who will be unaware of the study assignments.

Secondary Outcome Measures

1. Need for blood product transfusion within 48-hours post LVAD implantation
2. Operative safety outcomes: incidence of 30-day mortality (from the day of surgery to 30 days [+/- 3 days]), chest tube output in the first post-operative 24 hours, rate of post-operative re-exploration for bleeding
3. Incidence of allosensitization at 30-days, 6-months and 12-months post-LVAD implantation. Allosensitization is defined as calculated panel reactive antibody (cPRA) > 10%.
4. Readmission for heart failure (follow-up 1 year)
5. OHP, overall coagulation potential and overall fibrinolytic potential in the perioperative period
6. Major bleeding defined as an episode of suspected internal or external bleeding that results in one or more of the following: death, re-operation, hospitalization, transfusion of red blood cells according to INTERMACS definition.

Other Outcome Measures

1. Duration of surgery (skin incision to skin closure)
2. Duration of postoperative mechanical ventilation (length of time from intubation until patient is extubated)
3. Length of ICU stay (length of time from ICU admission from surgery until ICU discharge)
4. Length of hospital stay (length of time from surgery to hospital discharge)
5. Incidence of renal dysfunction defined by INTERMACS criteria
6. Incidence of 30-day mortality (from the day of surgery to 30 days [+/- 3 days])
7. Incidence of post-operative mortality within 6 months and 1 year

8. Device-related complications totaled at 30-days, 6-months and 12-months post-LVAD implantation.
9. Duration and amount of intraoperative and postoperative inhaled nitric oxide use

COLLECTION OF BASIC DATA/PATIENT CHARACTERISTICS

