Per standard of care, every subject receives a **transthoracic echocardiogram (TTE)** within 48 hours prior to LVAD implantation (baseline). These preoperative echocardiograms are reviewed and compared with echocardiograms at 30 (+/- 5) days, 6-months and 1-year post-LVAD implantation. The echocardiograms will be performed by staff cardiologists at UTHealth/Memorial Hermann Hospital-TMC and are regularly scheduled per standard of care. The staff cardiologists will not be aware of the treatment assignment of enrolled patients.

For each subject, the following echocardiographic parameters will be pulled from the electronic medical record and transferred to case report forms:

- left ventricular end-systolic diameter (LVESD)
- left ventricular end-diastolic diameter (LVEDD)
- left ventricular (LV) ejection fraction
- severity of mitral regurgitation (MR) based on a graded system
- RV ejection fraction (RVEF),
- RV end-diastolic dimension (RVEDD),
- RV end-systolic diameter (LVESD)
- RV stroke work index (RVSWI),
- tricuspid annular plane systolic excursion (TAPSE)
- severity of tricuspid regurgitation (TR)

Right heart catheterization is another standard diagnostic procedure for LVAD patients. The test evaluates the hemodynamics of LVAD patients. Right heart catheter hemodynamic variables are analyzed pre-LVAD implantation and compared with 30 (+/- 5) days, 6-months and 1-year post-LVAD implantation values as regularly scheduled care. All procedures will be performed by staff cardiologists at UTHealth/Memorial Hermann Hospital-TMC, who will not be aware of the treatment assignments.

For each subject, the following hemodynamic measurements will be pulled from the electronic medical record and transferred to case report forms:

- central venous pressure (CVP),
- pulmonary artery pressures (PAP): systolic and diastolic PAP,
- pulmonary capillary wedge pressure (PCWP),
- cardiac index (CI)
- pulmonary vascular resistance (PVR)
- right-atrial pressure (RAP)
- RAP: pulmonary capillary wedge pressure (PCWP) ratio

Laboratory parameters: Per standard of care, blood for routine biochemical and coagulation markers will be taken at prior to surgery (within 48 hours) and at follow-up visits (30 days, 6 months, 1 year). The electronic medical record will be used to ascertain the results of the following laboratory tests:

- complete blood count
- blood glucose
- hemoglobin A1c
- total cholesterol
- LDL cholesterol
- HDL cholesterol
- triglycerides
- creatinine

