Preparation of buffy coat: Buffy coat will be removed after the first spinning of the centrifuge and decanted into Eppendorf tubes. The remaining packed RBCs in tubes will be stored for later (storage at -80°C).

DETERMINATION OF ALLOANTIBODIES

The measurement and assessment of alloantibodies is now a standard of care test performed on patients scheduled for LVAD surgery. A single-bead antigen assay on the Luminex platform (One Lambda Inc., Canoga Park, CA) is used at the institution. Mean fluorescence intensity (MFI) >4,000 is considered the threshold of clinical significance. Whenever the alloantibodies and panel reactive antibody status (PRAs) are measured, the data will be transferred from the medical record to the case report forms.

Calculated PRA (cPRA) values will be obtained using the United Network of Organ Sharing cPRA calculator. Sensitization will be defined as cPRA >10%. LVAD-associated sensitization will be defined as cPRA >10% documented after LVAD implantation in patients with cPRA <10% before LVAD implantation.

STATISTICAL METHODS

We calculated a sample size of 140 patients (70 in each arm), which will provide 80% power to detect a 30% relative risk reduction for the composite primary outcome at 30 days. The intention-to-treat principle, in which all participants will be included in their assigned treatment groups regardless of actual surgical procedure performed, will guide all analyses.

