Data will be represented as frequency distributions and percentages. Values of continuous variables will be expressed as mean \pm standard deviation and median with interquartile range, as necessary. Continuous variables will be compared using independent samples t-tests or Wilcoxon rank-sum tests, where appropriate. Categorical variables will be compared by means of χ^2 tests or Fischer's exact test, where appropriate. Hemodynamic variables between ON-pump and OFF-pump procedures will be compared with Kruskal-Wallis tests. To analyze changes in echocardiographic and hemodynamic parameters and laboratory values, McNemar matched-pairs tests will be used to compare preoperative values to postoperative values after matching individual patient data. For all analyses, a $p < 0.05$ will be considered statistically significant. Kaplan-Meier analysis will be used to calculate survival along with a log-rank p value when comparing ON-pump and OFF-pump groups. Actuarial survival at 30-days, 6-months and 1-year post-implantation will be calculated by constructing life tables. All data will be analyzed using STATA 15 software (STATA, 2017, College Station, TX).

EXPECTED RESULTS AND IMPORTANCE OF THE STUDY

As LVADs become a more widely used and accepted treatment option for patients with refractory, end-stage heart failure, it will be necessary to further optimize outcomes and reduce the incidence of postoperative complications. We believe that using off-pump LVAD implantation will significantly reduce transfusion requirements, right ventricular dysfunction and alloantibody formation. We expect that in the off-pump group, there will be less exposure to blood products, which will lead to reduced immunosenzitization. If this research finds that off-pump use can decrease the morbidity and mortality in this patient population, it will greatly influence the manner in which these patients are managed. This would reduce hospitalizations and delays in subsequent transplant planning. This would not only be of great benefit to the patient but would significantly decrease health-care costs.

RISK AND BENEFITS

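### Pre-to-post changes in echocardiographic, haemodynamic and laboratory values are assigned to McNemar's test, which needs paired yes/no data; the listed values are continuous or graded (supportive analyses only)

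*Combined protocol and SAP*

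**What the plan says.** The STATISTICAL METHODS section deals with change in echocardiographic and haemodynamic parameters and laboratory values in a single sentence: "McNemar matched-pairs tests will be used to compare preoperative values to postoperative values after matching individual patient data". The other tests it names for comparing values are the independent-samples t-test, Wilcoxon rank-sum, chi-square, Fisher's exact and Kruskal-Wallis.

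The parameters are itemised under COLLECTION OF BASIC DATA/PATIENT CHARACTERISTICS. Most are plain measurements such as ejection fraction, TAPSE, wedge pressure and creatinine. Two are grades; one is entered as "severity of mitral regurgitation (MR) based on a graded system" and the other is tricuspid regurgitation severity.

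The same section gives the comparison visits. For catheterisation: "Right heart catheter hemodynamic variables are analyzed pre-LVAD implantation and compared with 30 (+/- 5) days, 6-months and 1-year post-LVAD implantation values". Preoperative echocardiograms are compared at the same three visits, and routine bloods are drawn at them. DEFINITION OF OUTCOME MEASURES adds a visit for TAPSE, which is "assessed using echocardiography prior to implantation (baseline), 14 (+/- 2 days) days post-implant, 30-days post-implant, 6-months and 1-year post-implant".

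That section also states one cut for a listed parameter: "we will collect also hemodynamic evidence of RV dysfunction with: a right-atrial pressure (RAP): pulmonary capillary wedge pressure (PCWP) ratio of ≥ 0.67". A second cut, cPRA above 10%, defines allosensitization, but cPRA is not among the listed parameters. Neither cut is mentioned in connection with McNemar's test.

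**The concern.** McNemar's statistic is built from two counts: patients who move from no to yes and patients who move from yes to no. A TAPSE in millimetres or a creatinine value gives neither count until someone chooses a threshold. The sentence supplies no threshold and says that values are to be compared.

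The within-patient analysis of serial right ventricular measures, TAPSE in particular, is therefore undefined. At analysis someone would have to replace the test or invent a cut for each parameter, possibly with the data in view. Reduced right ventricular dysfunction is one of the benefits the protocol expects from off-pump surgery, so these changes are likely to be reported even though they are not listed outcomes.

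**Working it through.** The plan gives no figure for this analysis, so there is nothing to reproduce. The check is of variable type, followed by one illustration.

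**1. Count of listed parameters** (COLLECTION OF BASIC DATA/PATIENT CHARACTERISTICS; systolic and diastolic pulmonary artery pressure counted separately, blood count as one entry, derived INR left out)

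| Group | Entries | Continuous | Graded | Yes/no |
|---|---|---|---|---|
| Echocardiography | 10 | 8 | 2 | 0 |
| Haemodynamics | 8 | 8 | 0 | 0 |
| Laboratory | 17 | 17 | 0 | 0 |
| Total | 35 | 33 | 2 | 0 |

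**2. What the test needs.** With b patients changing from no to yes and c from yes to no, McNemar's statistic is (b − c)² / (b + c). Without a cut, b and c do not exist. Only one of the 35 parameters, RAP:PCWP at 0.67 or more, has a relevant cut stated in the protocol, and it is not tied to this test.

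**3. Whether another named test covers the gap.** The t-test is specified for independent samples and the Wilcoxon test is the rank-sum version. Chi-square, Fisher and Kruskal-Wallis also compare independent groups. McNemar's is the only paired test named, so none remains for continuous or graded change.

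**4. Illustration of what a cut would cost.** None of these inputs is in the documents: normal data, within-patient shift 0.3 SD, pre/post correlation r = 0.5, cut at the baseline mean, two-sided 0.05, and 70 complete pairs (the most one arm could give).

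- Paired t: the SD of change is √[2(1 − r)] = √[2 × 0.5] = 1 SD, so the non-centrality is 0.3 × √70 / 1 = 2.51 and power is 0.70.
- McNemar: the expected share moving up across the cut is 0.230 and moving down is 0.112. The difference, 0.118, agrees with Φ(0.3) − 0.5. Power is 0.41 uncorrected and 0.32 exact.
- For r from 0.3 to 0.7: paired t 0.55 to 0.89; McNemar 0.35 to 0.50 uncorrected and 0.27 to 0.40 exact.
- Cut moved 1 SD below or above the mean (r = 0.5): McNemar 0.22 or 0.30 uncorrected, 0.16 or 0.23 exact.

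The answer depends on a cut that the plan does not give. With no true change and a fixed cut at the mean (r = 0.5), uncorrected McNemar rejects about 5% of the time and the exact version 3.0% at 70 pairs (3.6% at 140). The fault is therefore an undefined and inefficient analysis, not an excess of false positives at a pre-set cut.

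**The case against.** The strongest reply is that this is a misnamed test in a descriptive analysis. The sentence plainly intends within-patient pairing, and any analyst would substitute a paired test. The between-arm tests in the same section suit the data types, so the randomised comparison of TAPSE and pressures can go ahead. The power figures describe a dichotomised analysis that the plan never proposes, and every input is assumed. All of this stands, and it limits the point to supportive analyses. It does not remove the point, because the plan still names a test that cannot be run and leaves the substitute unstated.

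A second reply is that dichotomisation was intended. Nothing says so: the sentence compares values, and no cut is attached.

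Some stronger readings are tempting but not supported:

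- **That the post-operative visit is undefined.** The data-collection section names 30 days, 6 months and 1 year, and the outcome section adds day 14 for TAPSE. What is open is whether the tests are per arm or pooled.
- **That choosing McNemar creates a multiplicity problem.** Many parameters at several visits give many p-values under any test. A paired t-test would produce as many chance findings as McNemar, or more than its exact version.
- **That the primary outcome is compromised because TAPSE and RAP:PCWP appear under its heading.** Perioperative right ventricular failure is defined there by prolonged inotropes or an RVAD; these two measurements are collected alongside.
- **That the secondary outcome of overall hemostasis potential is caught by the words on laboratory values.** It is not in the laboratory list, it comes from additional research samples, and nothing assigns it to this test.

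**Conclusion.** The point holds in limited form. All 35 listed parameters, 33 continuous and 2 graded, are of the wrong type for the named test as recorded, and the section offers no paired alternative. The pre-to-post analysis cannot be carried out as written.

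The consequence stops at supportive within-patient analyses. None of the 35 is itself a listed primary, secondary or other outcome, and the 30-day composite is not analysed this way. The conclusion rests on the parameter list and on what McNemar's test requires, not on any assumed number. The power illustration shows the direction of the loss under one set of assumptions and should not be used to judge how serious the point is.

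**What to change.** Replace the McNemar sentence with text to this effect:

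1. Continuous values: paired t-test or Wilcoxon signed-rank test of within-patient change at 30 days, 6 months and 1 year, and also at day 14 for TAPSE.
2. Mitral and tricuspid regurgitation grade: a paired ordinal method, either signed-rank or a multi-category marginal-homogeneity test.
3. McNemar's test only for paired binary items whose cut is stated in advance, such as RAP:PCWP at 0.67 or more.
4. State whether the tests are per arm or pooled and label them supportive. Base any statement about off-pump versus on-pump surgery on between-arm comparisons, not on one arm changing significantly and the other not.

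The cost is one sentence growing to three or four. All values and visits are already in the protocol, and the sample size does not change.

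Optional, and not a correction of an error: adjust the between-arm comparison of these values for the baseline value already collected (ANCOVA). With 70 per arm, the unadjusted 95% confidence interval half-width is 1.977 × √(2/70) = 0.334 SD. At an assumed baseline correlation of 0.5 it becomes 0.334 × √(1 − 0.5²) = 0.289 SD. This needs slightly more programming and no new data.

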- aspartate aminotransferase (AST)
- alanine aminotransferase (ALT)
- total bilirubin
- albumin
- pre-albumin
- lactate,
- lactate dehydrogenase (LDH)
- prothrombin time (PT)
- activated plasma thromboplastin time (aPTT)

From this information the international normalized ratio (INR) will be calculated and recorded on case report forms.

PERIOPERATIVE VARIABLES

The medical record will be used to ascertain the following variables

- length of ICU stay
- length of hospital stay (LOS)
- total surgery time

- time-on-mechanical ventilation
- time on the CPB (min) (for “on pump” group only)
- number and type of concomitant cardiac procedures
- pharmacologic vasoactive and inotropic support (average daily dosage and duration of dobutamine, dopamine, epinephrine, norepinephrine and milrinone)
- duration and amount of perioperative use of inhaled nitric oxide
- total amount of bleeding (estimated based on mL of blood in the suction tank and gauzes in the operation room [each immersed gauze will be considered as 20 mL of blood] based on the evaluation by the anesthesiologist at the end of the operation)
- blood loss through the thoracic drains
- amount of received blood product units intraoperatively and in the 48-hours postoperatively will be recorded:
 - red blood cells (units)
 - fresh frozen plasma (units)
 - platelets (units)
 - cryoprecipitate (units)
- all postoperative complications following LVAD procedures
 - fever (defined as a body temperature above 38°C)
 - reoperation due to local infection
 - dehiscence or bleeding
 - sepsis
 - pneumonia
 - venous thromboembolism
 - acute coronary events in the first 30 days after surgery

COLLECTION OF LONGITUDINAL DATA

Patients will be followed for 1 year after surgery. All LVAD patients’ standard of care includes three planned follow-up assessments at 30 days (+/- 5 days), 6 months and 1 year after surgery. At each visit, the detailed medical history and clinical examination (including weight, height, blood pressure, heart rate, ECG, TTE, and blood draw) are performed. Relevant data will be collected from the medical record

and transferred to case report forms. Additional research blood draws will be done at the follow-up appointments.

SURGICAL TECHNIQUE

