As this study used two approved methods, it is a comparative effectiveness model. The risk to the patient is no more than that of any patient undergoing LVAD implantation. As the decision for eligibility for an off-pump is made based upon data and clinical evaluation, the risk of having to convert the procedure to on-pump is very small (less than 6 % of cases). The conversion is done to eliminate the risk of patients that are not able to tolerate the off-pump surgery. In our experience the off-pump insertion of the LVAD has been safe. Patients choosing to enroll in this trial are not at any additional risk as compared to that of having the procedure done outside of this trial. The benefit of participating in this trial is the contribution of novel data that is collected in a randomized fashion and will enable future cases to be decided upon quality evidence bases.

STUDY DATA COLLECTION AND STORAGE

Study data will be collected and managed using the REDCap electronic data capture tool (36). REDCap is a secure, web-based application designed to support data capture for research studies, providing: 1) an intuitive interface for validated data entry; 2) audit trails for tracking data manipulation and export procedures; 3) automated export procedures for seamless data downloads to common statistical packages; and 4) procedures for importing data from external sources.

All data will be stored on the password-protected computers. Only the principal investigator and co-investigators will have access to source documents, which will be password protected. All analysis will be completed on de-identified datasets.

DATA AND SAFETY MONITORING

The research team will follow the international, national, and institutional regulations and standards:

- Any patient that chooses to leave the study will be removed and their data up until that point will be retained in an de-identified fashion.
- Safety monitoring is accomplished through periodic review by the Primary Investigator, who will consult with the a Research Review team which will consist of a cardiac surgeon, a cardiovascular disease specialist, a biostatistician, and a pathologist. None of the Committee members will be directly involved in the study and will not work at our department.
- Further, this protocol will undergo continuing review by the Institutional Review Board at UTHealth.

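### The withdrawal rule ends outcome collection when a patient leaves and is not reconciled with the intention-to-treat rule

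*Combined protocol and SAP*

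**What the plan says.** The rule for leavers is one bullet under Data and Safety Monitoring: "Any patient that chooses to leave the study will be removed and their data up until that point will be retained", in de-identified form. It provides for no collection afterwards.

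Statistical Methods states intention-to-treat as the principle by which "all participants will be included in their assigned treatment groups regardless of actual surgical procedure performed, will guide all analyses". The only departure it names is crossover between techniques. The section has no rule for a missing 30-day outcome, no rule for censoring at withdrawal, and no dropout allowance beside the sample size.

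On sources, Collection of Longitudinal Data describes the 30-day, 6-month and 1-year visits as standard of care and adds: "Relevant data will be collected from the medical record". Echocardiography, catheterization and routine laboratory values are likewise taken from the electronic record. The main study-only procedure is the research blood draw, two extra vials per time point.

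Under Surgical Technique, the allocation envelope is opened in the operating room, after the surgeon has tested hemodynamic stability.

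**The concern.** The treatment is a single operation, and allocation is revealed during it. Every voluntary withdrawal is therefore post-treatment, and the outcome of the assigned operation still matters to the comparison. A rule that keeps data only up to leaving turns later outcomes into missing values.

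Two things are at stake. First, retained early data may not settle the 30-day composite. One criterion for right ventricular failure is intravenous inotropes for more than 14 days. A patient who leaves on day 10, still on inotropes and with no other component event, has an undetermined primary outcome. Second, the primary hypothesis extends to 1 year, and survival is to be compared by Kaplan-Meier and log-rank. Both assume that censoring is unrelated to prognosis. If patients leave because they are declining, censoring at withdrawal is informative, and the bias need not be equal in the two arms.

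**Working it through.** **Setting the passages side by side**

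| Question | What the plan provides |
|---|---|
| Does a leaver stay in the analysis set? | Not stated. The withdrawal bullet removes the patient; the intention-to-treat sentence includes all participants but elaborates only on the procedure performed. |
| Are data from before leaving kept? | Yes. |
| Are events after leaving collected? | Not provided for. |
| Would routine care record them? | Mostly yes: visits are standard of care and data come from the record. |
| Is stopping blood draws distinguished from withdrawing record permission? | No. A release of medical information is an inclusion criterion, but the effect of leaving on it is not stated. |
| Is there a missing-outcome or censoring rule? | No. |

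An analyst could exclude leavers by citing one section or include them by citing the other. Even if they are included, their later outcomes are absent.

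**Inputs for the illustration**

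- Sample size, from Statistical Methods: "We calculated a sample size of 140 patients (70 in each arm").
- Target, same section: "80% power to detect a 30% relative risk reduction for the composite primary outcome at 30 days".
- Alpha: 0.05, sidedness not stated; two-sided assumed.
- Control-arm rate of the composite: not stated.
- Withdrawal rate: not stated; 2% to 15% assumed.

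**The plan's own figure.** The 140 cannot be reproduced without a control rate. Solving the pooled two-proportion formula for 70 per arm, 80% power and p2 = 0.7 × p1 gives p1 = 0.752 and p2 = 0.526, a difference of 22.6 points. This implied rate is used below only as a reference; the absence of a stated control rate is a separate matter.

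**Effect on the range of possible results.** With k unknown outcomes in an arm of 70, that arm's risk is known only to within k/70.

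- k = 1: 1/70 = 1.4 points.
- k = 4 (about 6%): 4/70 = 5.7 points.
- k = 4 in both arms: from one extreme allocation of the unknowns to the other, the risk difference spans 8/70 = 11.4 points.

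For comparison, a 30% relative reduction is 22.6 points at the implied control rate, 0.30 × 40 = 12 points at an assumed 40%, and 0.30 × 30 = 9 points at an assumed 30%. These are extreme bounds. A patient who had a composite event before leaving is not unknown and does not count toward k.

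**Effect on power.** With n = 70 × (1 − d) per arm,

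power = Φ{[√n·(p1 − p2) − 1.96·√(2p̄(1 − p̄))] / √(p1(1 − p1) + p2(1 − p2))}, where p̄ is the mean of p1 and p2.

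| Assumed loss d | n per arm | Power |
|---|---|---|
| 0% | 70 | 80.0% |
| 2% | 68.6 | 79.2% |
| 5% | 66.5 | 77.9% |
| 10% | 63.0 | 75.6% |
| 15% | 59.5 | 73.2% |

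Power falls only slightly at low withdrawal. The case for a change therefore rests on possible bias and on the later outcomes.

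**The case against.** The strongest reply is that the two sections are compatible. The bullet sits under monitoring, and keeping the data suggests that *removed* means removed from further participation. The intention-to-treat sentence concerns crossover. Nothing says that leavers are dropped from the analysis. That stands: a reader might infer a direct contradiction, but the text does not establish one. It would be one only if removal meant removal from the analysis set.

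Other strong readings fail too:

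- *Events leave the numerator.* Events before leaving, including a stroke or renal replacement therapy within 30 days, are retained. Only later events are lost.
- *De-identification cuts the link to the record.* The plan describes a log linking the record number to the study code, lists that number among the information retained, and uses de-identified datasets for all analysis. It does not say that a leaver's link is destroyed.
- *Declining a research vial triggers removal.* The bullet covers leaving the study, and refusing a vial is not clearly that.
- *Unblinded patients will leave at different rates.* The plan specifies "individually randomized (1:1) controlled trial with blinded outcome assessment" and is silent on patient blinding. Differential withdrawal is possible but not shown.

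It is also fair to say that stopping collection when a patient leaves is not in itself an error, since use of the record needs permission. The consent form was not available to this review and may describe partial withdrawal. Finally, the study-only burden is light and much of the 30-day window is perioperative, so few primary outcomes may be lost.

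What survives is narrower. The protocol offers no follow-up after leaving, even for a patient who would allow it, and no analysis rule covers the resulting gaps.

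**Conclusion.** The point holds as an unreconciled gap. As written, the withdrawal bullet stops outcome collection after the assigned operation has been given, and Statistical Methods has nothing to repair this. Full intention-to-treat analysis is intended but not secured.

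The likely effect on the 30-day comparison is small: 1.4 points of uncertainty in an arm's risk per unknown status, and about 2 points of power (80.0% to 77.9%) at 5% loss. The exposure is greater for 6-month and 1-year mortality and heart failure readmission, where there is more time to leave and censoring could be informative. These figures rest on assumed withdrawal rates, a two-sided test and a control rate inferred from the sample size. They show scale and are not predictions. It is a worthwhile, inexpensive improvement, and not a flaw that invalidates the design.

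**What to change.** Replace the withdrawal bullet, and cross-refer to it from Statistical Methods, so that:

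1. every randomized patient stays in the assigned arm in the analysis set;
2. stopping research blood draws or other study procedures is distinguished from withdrawing permission to use the medical record;
3. unless that permission is explicitly withdrawn, composite components, vital status, transplant and readmissions continue to be abstracted from the record to 1 year, with the linking log kept for this purpose;
4. withdrawals are reported by arm with date and reason, and a best/worst-case sensitivity analysis is prespecified for unknown 30-day status.

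The survival analysis should also state how a patient who withdraws record permission is censored.

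The cost is protocol and consent wording, an IRB amendment and a little more record abstraction; no study visits are added. Some gaps will remain: events treated elsewhere may not appear in this hospital's record, and research assays cannot be recovered once blood draws stop.
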